9.2. Study Design

This will be a three-arm phase II study with historical references for each arm. The historical two-year RFS and corresponding event rates in these arms are assumed to be: myeloablative, 40% (0.46 per person year); non-myeloablative, 34% (0.54 per person year); and standard consolidation, 20% (0.80 per person year). The non-parametric Kaplan-Meier estimate will be used to monitor the relapse-free survival function in each cohort.

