9.4. Early Stopping Guideline for Futility and Simulations for Each Cohort

The simulation studies demonstrate the power for a sample size of 25 in each cohort. The study will be monitored for futility with a primary endpoint of two-year RFS. If the study meets the accrual goal of 10 patients per year per arm, 20 patients would be accrued by the time the first patient enrolled on study reaches the two-year efficacy endpoint. We will therefore monitor the study based on one-year RFS, knowing that if the one-year RFS is convincingly less than our targeted RFS at two years, the study would not meet its efficacy

objective and the trial should be halted. The non-parametric Kaplan-Meier estimate will be used to estimate the RFS function at one year.

The sample size of 25 and the study design operating characteristics assume a 2.5 year accrual period with an additional follow-up of one year. The null two-year RFS is 40% in the myeloablative group, 34% in the non-myeloablative group and 20% in the non-transplant cohort. We have designed each arm to stop early only if the posterior probability is 70% or higher that one-year RFS is less than that arm's null two-year RFS. Simulations were carried out with exponential survival and staggered patient entry. We assumed on average 10 patients will enter each arm of the study per year. Initial interim analyses occurred after 10 patients enrolled and was repeated every 5th patient to the maximum of 25. The interim analysis estimates of one-year RFS are based on analyses with an underlying Dirichlet process prior. We approximate the posterior distribution, which is actually a mixture of Beta distributions, the mixture depending on the amount of censoring, with a single Beta distribution. The parameters of this posterior Beta distribution are based on the number of failures and the effective sample size at one year, combined with the parameters of the prior.

The following tables summarize the operating characteristics under various scenarios for the underlying exponential RFS, based on 1000 simulations. The uncertainty of the null two-year RFS estimates are characterized with three priors: beta(2,3) in the myeloablative group (Table 5) and beta(2,4) in the non-myeloablative group (Table 6) and beta(1,4) in the non-transplant group (Table 7). This implies that our prior guess at the two year RFS for these three cohorts are respectively 40, 34 and 20%.

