The highlighted row gives the power of the study under the scenario where the median RFS is increased from 1.5 to 3.1 years in myeloablative patients, 1.3 to 3.1 years in non-myeloablative patients and 10.4 months to 18 months in the non-transplant patients. The 95% posterior intervals are the quantiles of the simulated one-year RFS corresponding to probabilities of .025 and .957. The interpretation is that the posterior probability that the estimate of one-year RFS lies in this interval is 95%.

These futility stopping rules are not excessively stringent: for instance the risk of not stopping the arm if the treatment is equal to the null hypothesis (the historical RFS rates), and therefore not effective, is approximately 50% in all three arms. However, we do not want to accept the null hypothesis and stop the trial if there is a reasonable probability that the experimental treatment may be effective. The treatment is relatively non-toxic, we are monitoring toxicities and adjusting doses accordingly, the risk of relapse is very high, and upon relapse the mortality rate is very high. Therefore, we are willing to accept the characteristics of these stopping rules.

Table 5

1year RFS	Prob Stop for Futility	Avg N	Estimated 1 yr RFS	lo 95% Post Int'l	hi 95% Post Int'l	Prob H0 Rejected (power)
0.20	0.95	11.22	0.185	0.0	0.36	0.0
0.30	0.77	14.26	0.264	0.0	0.48	0.01
0.40	0.46	18.51	0.360	0.1	0.60	0.09
0.50	0.16	22.68	0.487	0.2	0.72	0.36
0.60	0.06	24.07	0.588	0.3	0.80	0.69

Myeloablative: prior is beta(2,3) : Mean is 0.40

Table 6

1year RFS	Prob Stop for Futility	Avg N	Estimated 1 yr RFS	lo 95% Post Int'l	hi 95% Post Int'l	Prob H0 Rejected (power)
0.20	0.86	13.22	0.178	0.0	0.36	0.01
0.34	0.45	19.2	0.307	0.1	0.52	0.13
0.40	0.30	21.16	0.364	0.1	0.56	0.24
0.50	0.09	23.86	0.485	0.2	0.68	0.58
0.60	0.02	24.73	0.59	0.36	0.80	0.88

Non-myeloablative: prior is beta(2,4) : Mean is 0.34

Table 7

1year RFS	Prob Stop for Futility	Avg N	Estimated 1 yr RFS	lo 95% Post Int'l	hi 95% Post Int'l	Prob H0 Rejected (power)
0.10	0.92	12.35	0.081	0.0	0.20	0.0
0.20	0.52	18.17	0.168	0.0	0.36	0.08
0.30	0.20	22.25	0.277	0.0	0.48	0.36
0.40	0.06	24.2	0.390	0.10	0.60	0.74
0.50	0.01	24.87	0.502	0.32	0.68	0.95

Non-transplant : prior is beta(1,4) : Mean is 0.20

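### Tables 5-7 print a power for rejecting H0, but Section 9 gives no rejection rule, and the rows are one-year RFS while H0 is a two-year value

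*Combined protocol and SAP*

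**What the plan says.** Section 9.1.1 makes two-year RFS the primary objective, in three cohorts. Section 9.2 gives each cohort a historical reference and names an estimator: "The non-parametric Kaplan-Meier estimate will be used to monitor the relapse-free survival function in each cohort". Section 9.4 repeats the hypothesis values: "The null two-year RFS is 40% in the myeloablative group, 34% in the non-myeloablative group and 20% in the non-transplant cohort".

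Section 9.4 then presents operating characteristics: "The simulation studies demonstrate the power for a sample size of 25 in each cohort". Tables 5-7 list rows by one-year RFS, and their last column is headed "Prob H0 Rejected (power".

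Section 9 has two decision rules. The futility rule (9.3-9.4) tells an arm to "stop early only if the posterior probability is 70% or higher that one-year RFS is less than" the arm's null two-year RFS. The safety rule for acute GVHD (9.5) is written out count by count. There is no corresponding rule for declaring an arm positive, at one year or at two.

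**The concern.** A power figure is a property of a test. Without a stated test, two statisticians given the same 25 patients can reach different conclusions, and the choice can be made after the data are seen. One patient matters: in the non-myeloablative arm, moving the line from 12 to 13 of 25 changes the false-positive rate at a true rate of 34% from about 10% to about 5%.

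The second problem is the time point. The futility rule compares one-year RFS with a two-year null on purpose, because an arm already below the target at one year cannot be above it at two. That logic does not run in reverse: exceeding 40% at one year says little about exceeding 40% at two. If the unstated rejection rule also uses one-year RFS, it does not test the primary hypothesis.

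**Working it through.** **Inputs (Sections 9.2 and 9.4).** 25 patients per arm; nulls 0.40/0.34/0.20 at two years; priors "beta(2,3) in the myeloablative group (Table 5) and beta(2,4) in the non-myeloablative group (Table 6") and beta(1,4) in the non-transplant group; exponential RFS. Timing of looks: "Initial interim analyses occurred after 10 patients enrolled and was repeated every 5th patient to the maximum of 25". Results are "based on 1000 simulations", so the Monte Carlo SE is at most √(0.25/1000) ≈ 0.016.

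**1. Reproduce the futility column.** I used an exact binomial recursion with complete one-year data and looks at 10, 15 and 20. An arm stops if Pr(p < null) ≥ 0.70 under Beta(a + x, b + n − x), where x is the number relapse-free.

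| Table | Stop probability, recomputed | Printed |
|---|---|---|
| 5 | 0.95/0.75/0.44/0.19/0.06 | 0.95/0.77/0.46/0.16/0.06 |
| 6 | 0.88/0.45/0.27/0.09/0.02 | 0.86/0.45/0.30/0.09/0.02 |
| 7 | 0.91/0.54/0.21/0.06/0.01 | 0.92/0.52/0.20/0.06/0.01 |

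All are within 0.03, and average N is within 0.4, so the design has been read correctly.

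**2. Is the power column one minus the stop probability?** No. In the rows where one-year RFS equals the null figure, one minus the printed stop probability is 0.54/0.55/0.48. The printed rejection probabilities are 0.09/0.13/0.08. A further criterion was applied.

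**3. Is it a success count out of 25?** P(not stopped and X ≥ c), by row:

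| Table | c | Recomputed | Printed | Worst gap |
|---|---|---|---|---|
| 5 | 14 | 0.000/0.006/0.076/0.337/0.722 | 0.0/0.01/0.09/0.36/0.69 | 3.2 points |
| 6 | 12 | 0.001/0.102/0.262/0.646/0.917 | 0.01/0.13/0.24/0.58/0.88 | 6.6 points |
| 6 | 13 | 0.000/0.048/0.152/0.497/0.844 | as above | 8.8 points |
| 7 | 9 | 0.000/0.045/0.316/0.717/0.941 | 0.0/0.08/0.36/0.74/0.95 | 4.4 points |
| 7 | 8 | 0.002/0.103/0.469/0.828/0.971 | as above | 10.9 points |

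Table 6 at c = 12 misses by more than 4 SE (0.066/0.015). Its printed values are above c = 12 in the 0.34 row and below it in the 0.60 row, which no change of count can produce. Table 7 at c = 9 misses its 0.20 row by about 5 SE (0.035/0.0066). Table 5 at c = 14 is only 2.3 SE out at worst. Without the futility looks the best worst-row gaps are 4.2, 7.5 and 3.7 points. No single posterior, Wald, one-sample log-rank or exponential cutoff that was tried reproduced all three tables.

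**4. Which time point?** With hazard λ = −ln(S₂)/2, the nulls give 0.46, 0.54 and 0.80 per person-year, as printed in 9.2, so they are two-year values. One-year RFS under the same model is √S₂: √0.40 = 0.63, √0.34 = 0.58, √0.20 = 0.45.

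In the other direction, a table row S₁ has two-year RFS S₁². The top row of Table 5 gives 0.60² = 0.36, below its own null of 0.40, yet it carries a rejection probability of 0.69. In Tables 6 and 7 only the top rows exceed their nulls (0.36 against 0.34; 0.50² = 0.25 against 0.20).

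As an illustration, apply the nearest counts (14, 12 and 9 of 25) to one-year status when the two-year null is exactly true. They reject with probability 0.83, 0.89 and 0.86.

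**5. The targets.** Median m gives S₂ = 0.5^(2/m). For 3.1 years S₂ = 0.64 and one-year RFS is 0.80; for 18 months S₂ = 0.40 and one-year RFS is 0.63. Tables 5 and 6 stop at 0.60, so neither has a row for the 3.1-year target at either time point.

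**The case against.** The best defence is that a rule existed and was simply not reported. Section 9.4 describes staggered entry, Kaplan-Meier estimation and an effective sample size, so the rule need not be a count out of 25. Freeing the denominator supports this: 8 of 23 fits Table 7 within 1.3 points, 9 of 18 fits Table 6 within about 2, and 13 of 23 fits Table 5 within 2.3. These fits are after the fact and identify nothing, but they do show that the mismatch in step 3 depends on assuming 25 complete patients. A reader might infer that no rule was used or that the column is wrong; the documents do not support that. The defect is that the rule is not written.

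A reader might also take 0.09/0.13/0.08 as the arms' type I error rates and combine them across arms. That does not hold either. Those rows have one-year RFS equal to the null figure, hence two-year RFS of 0.16/0.12/0.04, far below the nulls. The cohorts also have separate references, and the plan claims no family-wise error.

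The row label could be a slip for two years. But the estimate column also says one year, and the text describes the intervals as intervals for one-year RFS.

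Finally, this is a phase II study whose aim is to evaluate RFS, and a purely descriptive report would need no test. That is fair, but such a plan would not print power for rejecting H0.

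**Conclusion.** The point holds. Section 9 prints power without a rejection rule. The column cannot be matched to one minus the stop probability or, for Tables 6 and 7, to any fixed count out of 25 complete patients; for Table 5 the mismatch is weak. Independently of that, the rows are one-year values and the nulls are two-year values, so under the plan's own exponential model the printed power does not apply to the primary hypothesis.

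This does not show that 25 patients per arm are too few: under the two-year rule set out in the fix, power at the protocol's targets is reasonable. Nor is the borderline range the same in every arm; in the non-transplant arm it lies around 8 to 9 of 25. The recalculations assume exponential RFS and complete data at the stated time point.

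**What to change.** In 9.2 or 9.4, state one success rule per arm with its time point (two years from the RFS start in 9.1.1), its threshold and its false-positive rate. Say how patients censored before two years are handled. Then recompute the last column of Tables 5-7 at two-year RFS values, including the nulls and the targets.

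One workable rule rejects H0 if the posterior probability that two-year RFS exceeds the arm's null is at least 0.90. It uses the printed priors, which 9.4 already describes as guesses at two-year RFS. With 25 complete patients:

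| Arm | Count needed | Posterior (one fewer) | False-positive rate | Power at target |
|---|---|---|---|---|
| Myeloablative (0.40 vs 0.64) | 14 | 0.929 (0.864) | 7.8% | 0.85 |
| Non-myeloablative (0.34 vs 0.64) | 13 | 0.949 (0.897) | 4.8% | 0.92 |
| Non-transplant (0.20 vs 0.40) | 9 | 0.951 (0.892) | 4.7% | 0.72 |

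These are plain binomial tails with no futility stop. At the two-year nulls the one-year futility rule, with complete data, would stop only about 3.5/2.4/3.0% of arms, so it changes little. The 0.90 cutoff is a choice, and 12 of 25 in the non-myeloablative arm falls just short of it. The sponsor may fix another cutoff in advance and restate power for it.

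The cost is one paragraph and a rerun of one column, with no added patients or visits. The final reading must wait for two-year status rather than the one-year follow-up assumed in the simulations; the three-year follow-up in Section 5.4 already covers this.

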9.5. Early Stopping Rules for Safety

This study will monitor acute grade III/IV GVHD in the two transplant arms. If it becomes evident that the proportion of acute grade III/IV GVHD convincingly exceeds 10%, the study will be halted for a safety consultation. The stopping rule will be applied to both transplant arms and will hold enrollment if the posterior probability of toxicity more than

0.10 is 75% or higher. The prior for this monitoring rule is $\beta(1,9)$. This means that our prior guess at the proportion of acute grade III/IV GVHD is 10%, and there is 90% probability that this proportion is between 0.57% and 28.3%. The operating characteristics of the stopping rule are given in the Table 8 and are based on 5000 simulations:

Toxicity stopping rule:

- Serious AE in 2 out of 2 patients. $\Pr(\text{Risk} > 0.1 | \text{Data}) = 0.91$
- Serious AE in 2 out of 3 patients. $\Pr(\text{Risk} > 0.1 | \text{Data}) = 0.889$
- Serious AE in 2 out of 4 patients. $\Pr(\text{Risk} > 0.1 | \text{Data}) = 0.866$
- Serious AE in 2 out of 5 patients. $\Pr(\text{Risk} > 0.1 | \text{Data}) = 0.842$
- Serious AE in 2 out of 6 patients. $\Pr(\text{Risk} > 0.1 | \text{Data}) = 0.816$
- Serious AE in 2 out of 7 patients. $\Pr(\text{Risk} > 0.1 | \text{Data}) = 0.789$
- Serious AE in 2 out of 8 patients. $\Pr(\text{Risk} > 0.1 | \text{Data}) = 0.762$
- Serious AE in 3 out of 9 patients. $\Pr(\text{Risk} > 0.1 | \text{Data}) = 0.902$
- Serious AE in 3 out of 10 patients. $\Pr(\text{Risk} > 0.1 | \text{Data}) = 0.885$
- Serious AE in 3 out of 11 patients. $\Pr(\text{Risk} > 0.1 | \text{Data}) = 0.867$
- Serious AE in 3 out of 12 patients. $\Pr(\text{Risk} > 0.1 | \text{Data}) = 0.848$
- Serious AE in 3 out of 13 patients. $\Pr(\text{Risk} > 0.1 | \text{Data}) = 0.828$
- Serious AE in 3 out of 14 patients. $\Pr(\text{Risk} > 0.1 | \text{Data}) = 0.807$
- Serious AE in 3 out of 15 patients. $\Pr(\text{Risk} > 0.1 | \text{Data}) = 0.786$
- Serious AE in 3 out of 16 patients. $\Pr(\text{Risk} > 0.1 | \text{Data}) = 0.764$
- Serious AE in 4 out of 17 patients. $\Pr(\text{Risk} > 0.1 | \text{Data}) = 0.888$
- Serious AE in 4 out of 18 patients. $\Pr(\text{Risk} > 0.1 | \text{Data}) = 0.873$
- Serious AE in 4 out of 19 patients. $\Pr(\text{Risk} > 0.1 | \text{Data}) = 0.858$
- Serious AE in 4 out of 20 patients. $\Pr(\text{Risk} > 0.1 | \text{Data}) = 0.842$
- Serious AE in 4 out of 21 patients. $\Pr(\text{Risk} > 0.1 | \text{Data}) = 0.825$
- Serious AE in 4 out of 22 patients. $\Pr(\text{Risk} > 0.1 | \text{Data}) = 0.807$
- Serious AE in 4 out of 23 patients. $\Pr(\text{Risk} > 0.1 | \text{Data}) = 0.789$
- Serious AE in 4 out of 24 patients. $\Pr(\text{Risk} > 0.1 | \text{Data}) = 0.77$
- Serious AE in 4 out of 25 patients. $\Pr(\text{Risk} > 0.1 | \text{Data}) = 0.75$

Table 8

True Tolerability Risk	Prob. Declare Treatment Not Tolerable	Avg. Sample Size
0.02	1.5%	24.8
0.05	8.5%	23.7
0.10	34.8%	20.2
0.15	62.8%	16.0
0.20	81.8%	12.6
0.25	92.8%	9.7
0.30	97.8%	7.6

Operating characteristics of stopping rule based on 5000 simulations.

10. Data Safety and Monitoring Plan

The study PI will be responsible for the conduction of the study, including the monitoring of the study’s safety and oversight of the data collection. The PI will follow the Data Safety and Monitoring plan outlined in the Sidney Kimmel Comprehensive Cancer Center’s policy. This trial is designated as a category 1 protocol based on the risk and monitoring needs.

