5.2.2. Definitions of Hematologic Toxicity

Critical neutropenia or thrombocytopenia is defined by a neutrophil count $<100/\text{mm}^3$ or a platelet count $<10,000/\text{mm}^3$. Persistent critical cytopenias are those that last for greater than 3 weeks.

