10.1. Data Reporting

This is a DSMP Level I High-Medium Risk study under the SKCCC Data Safety Monitoring Plan (9/22/2011). The Clinical Research Office QA Group will perform an audit after the first subject has been treated and then periodically depending on the rate of accrual and prior audit results. All trial monitoring and reporting will be reviewed annually by the SKCCC Safety Monitoring Committee. The PI is responsible for monitoring the study. Data must be reviewed to assure the validity of data, as well as, the safety of the subjects. The PI will also monitor the progress of the trial, review safety reports, and clinical trial efficacy endpoints and to confirm that the safety outcomes favor continuation of the study. The PI will be responsible for maintaining the clinical protocol, reporting adverse events, assuring that consent is obtained and documented, reporting of unexpected outcomes, and reporting the status of the trial in the continuing renewal report submitted to the IRB and to the trial monitoring review group. Content of the continuing renewal report at a minimum should include year-to-date and full trial data on: accrual and eligibility, protocol compliance, treatment administration, toxicity and ADR reports, response, survival, regulatory compliance, compliance with prearranged statistical goals. The report should be submitted in a timely manner according to the schedule defined by Johns Hopkins Medicine Institutional Review Board."

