10.6. Adverse Drug Reaction and Toxicity Monitoring

The study team (research nurse, study coordinator or attending) will assign toxicity scores using the NCI common Toxicity Criteria version 4.03, weekly through the first cycle of therapy and at least every cycle thereafter. A copy of the CTC version 4.0 is available at the CTEP home page (<http://ctep.info.nih.gov>). If an unexpected and serious toxicity occurs that would result in patients being subjected to unacceptable risk, the trial will be placed on hold while this toxicity is investigated.

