10.7. Toxicity Reporting

The Principal Investigator is responsible for the ongoing safety evaluation of the study. Unanticipated events will be reported to IRB as per JHMIRB policy 103.6b, *Organization Policy on reports of Unanticipated Problems Involving Risks to Participants or Others*. Expectedness of events will be determined by the product inserts for 5AC and GM-CSF. All other events will be logged on a Master AE Log as per SKCCC policy.

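### The only numeric safety rule covers GVHD in the two transplant arms, so the consolidation arm, and serious expected toxicity such as myelosuppression, have no dedicated aggregate toxicity trigger

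*Combined protocol and SAP*

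**What the plan says.** Section 9.1.1 defines three cohorts: myeloablative transplant, non-myeloablative transplant and standard consolidation. Section 9.4 plans 25 patients in each, at about 10 per arm per year.

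The formal safety rule is in 9.5: "This study will monitor acute grade III/IV GVHD in the two transplant arms". It covers those two arms only and pauses enrollment once the posterior probability of a rate above the limit is high enough; limit and cut-off are given as "0.10 is 75% or higher". The prior is beta(1,9), explained as a 10% prior guess for acute grade III/IV GVHD. The boundary list beneath it is worded differently: every line counts a Serious AE among the patients treated.

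The trial-wide hold is in 10.6: "If an unexpected and serious toxicity occurs that would result in patients being subjected to unacceptable risk, the trial will be placed on hold". Section 10.7 adds: "Expectedness of events will be determined by the product inserts for 5AC and GM-CSF". Section 7.4 lists neutropenia, thrombocytopenia, anemia and febrile neutropenia among the known toxicities of 5AC. Section 7.2.1 reports that an earlier maintenance schedule was poorly tolerated because of neutropenia.

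Section 5.2.2 defines a term that no rule in the protocol then uses: "Persistent critical cytopenias are those that last for greater than 3 weeks". Section 10.1 describes the aggregate review: "All trial monitoring and reporting will be reviewed annually by the SKCCC Safety Monitoring Committee".

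Section 9.4 accepts roughly a 50% chance of not stopping an ineffective arm, and gives as part of the reason: "The treatment is relatively non-toxic, we are monitoring toxicities and adjusting doses accordingly".

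**The concern.** The plan treats three arms but sets a toxicity boundary in two of them, for one event. That event is a transplant complication, so it cannot serve as a safety measure for the consolidation arm. The all-arm hold does not fill the gap, because it is written for unexpected toxicity and the toxicity that the protocol itself discusses most as a tolerability limit is a listed one.

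If the combination proved too myelosuppressive, the written procedures would hold, reduce or remove patients one at a time. No stated rate of serious events would oblige anyone to pause the consolidation arm. The futility section leans on toxicity monitoring to justify a permissive rule, and in this arm no toxicity-rate rule supports that argument.

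**Working it through.** **1. Reproduce the rule.** Inputs from 9.5: prior beta(1,9), limit 0.10, cut-off 0.75. After x events in n patients the posterior is beta(1 + x, 9 + n − x). The boundary is the smallest x with Pr(rate > 0.10) ≥ 0.75.

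- 2 of 2: beta(3,9) gives 0.910. 2 of 8: beta(3,15) gives 0.762.
- 3 of 9: beta(4,15) gives 0.902. 3 of 16: beta(4,22) gives 0.764.
- 4 of 25: beta(5,30) gives 0.750.

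All 24 printed lines match (2 events at n = 2–8, 3 at 9–16, 4 at 17–25). So does the prior's 90% interval, 0.57% to 28.3%.

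**2. Reproduce Table 8.** An exact binomial recursion that checks the boundary after every patient, to n = 25, with each outcome known before the next patient enters:

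| True rate | Stop, Table 8 | Stop, exact | Avg N, Table 8 | Avg N, exact |
|---|---|---|---|---|
| 0.02 | 1.5% | 1.3% | 24.8 | 24.8 |
| 0.05 | 8.5% | 8.8% | 23.7 | 23.7 |
| 0.10 | 34.8% | 34.1% | 20.2 | 20.2 |
| 0.15 | 62.8% | 62.1% | 16.0 | 16.2 |
| 0.20 | 81.8% | 82.1% | 12.6 | 12.5 |
| 0.25 | 92.8% | 92.9% | 9.7 | 9.7 |
| 0.30 | 97.8% | 97.6% | 7.6 | 7.7 |

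Pooling the two transplant arms to n = 50 gives 43.4% at a rate of 0.10, so Table 8 describes a rule run per arm. The arithmetic of 9.5 is sound; the issue is coverage.

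**3. Coverage, from the text.**

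| Provision | Arms | What sets it off | Toxicity-rate trigger? |
|---|---|---|---|
| 9.5 text and prior | Two transplant arms | Acute grade III/IV GVHD | Yes |
| 9.5 boundary list, read literally | Two transplant arms | Serious AE | Yes |
| 10.6 with 10.7 | All | Toxicity both unexpected and serious | No numeric limit |
| 5.1–5.3 | All | One patient's toxicity | No; acts on that patient |
| 9.4 futility | All | Relapse or death | No |
| 10.1 | All | Investigator monitoring, audits, annual review | No numeric limit |

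The consolidation arm is outside 9.5 on either reading of the event.

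**4. Scale in one arm of 25.** The 20–30% rates are illustrative; the documents give no rate for serious toxicity of this combination. Expected events without a rule are 25 × rate. With a rule they are rate × average N. Two timings are shown: outcomes known at once (step 2), and a simulation with 10 entries per year, event times uniform over one year (an assumption) and enrolled patients as denominator.

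| Rate | No rule | Immediate: avg N, events | Spread over a year: avg N, events |
|---|---|---|---|
| 0.20 | 5.0 | 12.5, 2.5 | about 18, 3.7 |
| 0.25 | 6.3 | 9.7, 2.4 | about 16, 4.0 |
| 0.30 | 7.5 | 7.7, 2.3 | about 14, 4.2 |

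Spread over six months, average N is about 16, 13 and 11. Timing therefore removes much of the saving that Table 8 would suggest.

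**5. The GVHD limit does not transfer.** Section 7.4 quotes 16% for febrile neutropenia and 32% for neutropenia in earlier 5AC studies. Run against those rates, the 10% boundary would stop an arm 66.8% and 98.5% of the time.

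**6. Time between reviews.** At 10 patients per arm per year, about 10 patients per arm (3 × 10 = 30 overall) can enter between annual committee reviews, if no other oversight intervenes.

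**The case against.** The best defence is that oversight is layered. Escalation under 5.1 requires two consecutive cycles without an SAE, and 5.2 and 5.3 hold, reduce or remove affected patients. Section 10.1 requires the investigator to confirm that safety outcomes favor continuation, in every arm and without limiting this to unexpected events. There are audits from the first treated subject onward, and the cancer center's own monitoring plan, which is not reproduced here, may add more. All of this stands. A reader might infer that the consolidation arm has no safety oversight, or no chance of being halted for toxicity; the documents do not support that. What is missing is a pre-specified rate that compels a pause.

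A reader might also infer that an excess of treatment-related deaths meets no written trigger. That is wrong: 9.1.1 defines RFS as time to relapse or death, so deaths enter the futility rule in all three arms. The rule is a blunt instrument for this purpose. In Table 7 a consolidation arm with one-year RFS of 0.40 stops 6% of the time, and at 0.30 it stops 20% of the time. Non-fatal toxicity does not enter it at all.

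Nor is it safe to say flatly that the transplant arms have no trigger for myelosuppression. Read literally, the Serious AE list would count it whenever it met the SAE definition in 10.5. The stated event, limit and prior make GVHD the more likely intent, but the text conflicts.

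Finally, the poor tolerability reported in 7.2.1 was for 75 mg/m² over seven days. This trial starts at 37.5 mg/m² over five, and the same section reports the fewest serious adverse events with 75 mg/m² over five days. The documents do not show that this regimen is too myelosuppressive. They also do not show how the inserts would class prolonged or fatal cytopenia; that it would count as expected is an inference from the list in 7.4.

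**Conclusion.** The gap holds as one of coverage. The consolidation arm has no numeric toxicity trigger, and serious expected toxicity has no dedicated aggregate trigger in any arm on the GVHD reading of 9.5. On the literal reading of its list, the transplant arms would have one and the consolidation arm still would not. The two parts of 9.5 must be reconciled whichever was meant.

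The size depends on rates the documents do not give. At illustrative rates of 20% to 30%, a rule of this form would cut expected events in an arm of 25 from 5.0–7.5 to 2.3–2.5 if outcomes were immediate, or to 3.7–4.2 if they were spread evenly over a year. A reader might take Table 8 as the performance of an added rule. It is not, because it matches a calculation in which each outcome is known before the next enrolment. The plan should be changed, since 9.4 rests part of its futility argument on toxicity monitoring.

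**What to change.** Reconcile 9.5 with 9.4, 10.6 and 10.7:

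- State one event for the 9.5 boundary list, so that the list, the text and the prior agree.
- Extend an aggregate posterior-probability rule of the same form to the consolidation arm and to expected serious toxicity. The sponsor sets the event and the tolerable rate. A crossing goes promptly to the existing Safety Monitoring Committee instead of waiting for the annual review.
- Reconcile the restriction to unexpected toxicity in 10.6 with that sentence's own criterion of unacceptable risk.
- Recompute the operating characteristics for the chosen event, limit and event timing, with staggered entry at the planned accrual. Do not carry over Table 8.

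The cost is protocol wording, a boundary table and a short simulation, using adverse event and blood count data already collected and a committee already in place. The downside is some chance of a false pause: 34.8% at a true 10% rate under the present GVHD limit, and a different figure for whatever limit is chosen.

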10.5. Serious Adverse Event (SAE) Definition

As defined by the FDA CFR 312, a serious adverse event is one, occurring at any dose (including overdose), that results in any of the following:

1. Death
2. Life-threatening illness
3. Inpatient hospitalization or prolongation of existing hospitalization
4. Persistent or significant disability or incapacity
5. A congenital anomaly or birth defect
6. An important medical event
7. Pregnancy

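### Section 9.5 names two different events for one safety stopping rule: acute grade III/IV GVHD in the text, Serious AE in all 24 boundary lines

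*Combined protocol and SAP*

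**What the plan says.** Section 9.5 of the combined protocol and SAP opens with the monitored event: "This study will monitor acute grade III/IV GVHD in the two transplant arms". It ties the limit to that event: "If it becomes evident that the proportion of acute grade III/IV GVHD convincingly exceeds 10%, the study will be halted for a safety consultation". The beta(1,9) prior is described as a prior for the same proportion. The sentence that triggers the hold is looser. It refers only to toxicity, and enrolment is held if the posterior probability of a risk above "0.10 is 75% or higher".

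The list headed as the toxicity stopping rule then gives one line for each number of patients from 2 to 25. It runs from "Serious AE in 2 out of 2 patients" to "Serious AE in 4 out of 25 patients". None of the 24 lines mentions GVHD. The first column of Table 8 is headed True Tolerability Risk.

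Section 10.5 defines a serious adverse event in the regulatory sense. The list includes death, life-threatening illness, "Inpatient hospitalization or prolongation of existing hospitalization", important medical events and pregnancy, with no requirement that the event be related to treatment or to GVHD. Section 5.1 uses SAE for a different decision, eligibility for dose escalation.

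**The concern.** A stopping rule has to name one countable event, and this one names two that are not interchangeable. An unrelated hospital admission is a serious adverse event under section 10.5 but is not acute grade III/IV GVHD. Two such admissions among the first eight patients of a transplant arm would meet the listed boundary, while under the paragraph they would count for nothing. Two people applying section 9.5 to the same data could therefore reach opposite decisions on holding enrolment.

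The calibration is also at stake. The 10% limit and the prior are given for GVHD. The plan offers no limit, prior or expected rate for SAEs, so under the literal reading nobody can say which row of Table 8 describes the trial.

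**Working it through.** **Inputs.** From section 9.5: prior beta(1,9), limit 0.10, posterior cut-off 0.75, and boundary lines for n = 2 to 25. From section 9.4: 25 patients per arm. The SAE rate per patient is not given and is treated as an assumption.

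**Step 1: the boundary.** With x events in n patients the posterior is Beta(1 + x, 9 + n − x). The boundary is the smallest x with Pr(risk > 0.10) ≥ 0.75.

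- 1 of 1: Beta(2, 9) gives 0.736, below 0.75, so there is no boundary at n = 1.
- 2 of 2: Beta(3, 9) gives 0.910 (printed 0.91).
- 2 of 8: 0.762. 3 of 9: 0.902. 3 of 16: 0.764. 4 of 17: 0.888. All as printed.
- 4 of 25: Beta(5, 30) gives 0.7504 (printed 0.75). 3 of 25 gives only 0.554.

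The boundary is 2 events for n = 2–8, 3 for n = 9–16 and 4 for n = 17–25. All 24 printed lines agree. The 5% and 95% quantiles of beta(1,9) are 0.57% and 28.3%, also as printed.

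**Step 2: Table 8.** Exact recursion over n = 1 to 25, checking the boundary after each patient:

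| True risk | Stop, printed | Stop, exact | Avg N, printed | Avg N, exact |
|---|---|---|---|---|
| 0.02 | 1.5% | 1.3% | 24.8 | 24.8 |
| 0.05 | 8.5% | 8.8% | 23.7 | 23.7 |
| 0.10 | 34.8% | 34.1% | 20.2 | 20.2 |
| 0.15 | 62.8% | 62.1% | 16.0 | 16.2 |
| 0.20 | 81.8% | 82.1% | 12.6 | 12.5 |
| 0.25 | 92.8% | 92.9% | 9.7 | 9.7 |
| 0.30 | 97.8% | 97.6% | 7.6 | 7.7 |

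Every probability agrees to within 0.8 percentage points. With 5000 simulations the standard error at 34.8% is √(0.348 × 0.652 / 5000) = 0.7 points, so this is simulation noise.

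**Step 3: the literal reading.** Because the boundary is 2 events throughout n = 2–8, the chance of a hold by n ≤ 8 is simply 1 − (1 − p)^n − n p (1 − p)^(n−1). At p = 0.20 and n = 5 this is 1 − 0.328 − 0.410 = 0.263. The n = 25 column uses the recursion of step 2.

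| Assumed SAE rate | Hold by 5 | Hold by 8 | Hold by 25 | Avg N |
|---|---|---|---|---|
| 10% | 8% | 19% | 34% | 20.2 |
| 20% | 26% | 50% | 82% | 12.5 |
| 30% | 47% | 74% | 98% | 7.7 |
| 40% | 66% | 89% | 99.8% | 5.3 |
| 50% | 81% | 96% | >99.9% | 4.1 |

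Solving the other way, a 95% chance of a hold needs an SAE rate of about 66% by 5 patients, 47% by 8, or 27% by 25.

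These figures assume that each patient's status is known before the next patient enters. Treatment is planned for 12 cycles (section 5.3) and about 10 patients per arm per year are expected (section 9.4). Events may therefore appear after later patients have enrolled, and actual enrolment at a hold could exceed the averages shown.

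**The case against.** The strongest reply is that context settles the meaning. The paragraph directly above the list names acute grade III/IV GVHD as the monitored event, as the event with the 10% limit and as the subject of the prior. All 24 posteriors follow from that prior and limit, so the list looks like the GVHD rule printed under a generic label. Other serious toxicity has its own provisions in sections 5.2.4 and 10.6. This stands as evidence that GVHD is the likelier intent. It does not remove the conflict: the list is the only place that gives the triggering counts, and it uses a term that section 10.5 defines differently.

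Three further limits also stand. First, the consequence is a hold on enrolment for a safety consultation, where the type of event would come to light, and not automatic termination of an arm. Second, a reader might infer that staff would work from the list alone; no section says so, or says that the list overrides the paragraph. Third, a reader might infer that Table 8 is valid under only one reading. It holds for any yes/no event monitored with this boundary. The event label determines which row is relevant, not whether the table is correct.

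**Conclusion.** Wrong as written: an internal inconsistency in a stopping rule. The boundaries, posteriors, prior interval and operating characteristics are arithmetically sound; the fault is confined to the event label. The 10% reference is justified in the plan only for acute grade III/IV GVHD.

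The size of the effect under a literal SAE reading is conditional. Over assumed SAE rates of 10% to 40%, the chance of a hold runs from 8% to 66% by 5 patients and from 34% to 99.8% by 25, given immediate knowledge of each patient's status. A reader might infer that a transplant arm would almost surely be halted after a handful of patients. The documents do not support that. They give no SAE rate, and at 20% to 30% the chance of a hold by 5 patients is only 26% to 47%. The label conflict itself rests on no assumption.

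**What to change.** Reconcile the paragraph of section 9.5, the 24 boundary lines and the first column of Table 8 so that all name the same event, and use that name in the sentence that triggers the hold. If the event is acute grade III/IV GVHD, as the paragraph, limit and prior indicate, this is relabelling: every boundary, posterior and operating characteristic stays as printed. If serious adverse events are also to be monitored, state that as a separate rule with its own limit, prior, boundary and operating characteristics, based on a stated expected SAE rate.

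The relabelling costs a wording amendment and no new calculation. A separate SAE rule would need a justified reference rate and a short additional calculation. Neither changes the sample size.
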